4.1 Number of Patients

Approximately 1200 patients will be randomized (400 patients per arm) from approximately 200 centers in the United States.

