5.1.1.1.3 Statistical Methodology

The methodologies defined below apply as specified to individual endpoints defined in this SAP. All statistical tests will be 2-sided hypothesis tests performed at the 5% level of significance for main effects. All confidence intervals will be 2-sided 95% confidence intervals, unless stated otherwise.

Table 5-2 Statistical Methodology

Methodology	Description
M1 Categorical counts	
 • Number of participants in individual categories 
 ○ Participants with ≥ 1 qualifying event counted once per individual category
M2 Categorical descriptives	
 • Number and percentage of participants in individual categories 
 ○ Participants with ≥ 1 qualifying event counted once per individual category • N1 if proportion denominator \neq number of participants in the population (standard percentage denominator) 
 ○ N1 = participants with non-missing baseline value
M3 PCS descriptives	
 • Number and percentage of participants meeting potentially clinically significant (PCS) criteria 
 ○ Participants with ≥ 1 qualifying event counted once per PCS category • Percentage denominator = number of participants with all non-missing non-PCS baseline and ≥ 1 non-missing postbaseline assessment 
 ○ Unevaluable assessments considered missing
M4 Shift analysis	
 • Number and percentage of participants in individual baseline and postbaseline categories • Percentage denominator = number of participants in individual baseline categories • N1 = participants with non-missing values at both baseline and the specified postbaseline analysis visit
M5 Continuous descriptives	
 • N1, mean, standard deviation (SD), median, minimum, maximum • N1 = participants with non-missing value
M6 CFB descriptives	
 • Continuous descriptives for baseline, postbaseline, and change from baseline (CFB) values • N1 = participants with non-missing values at both baseline and the specified postbaseline analysis visit

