Number of attacks treated with study treatment per month ¹	
 ≥ 8 ≥ 6 and < 8 ≥ 4 and < 6 ≥ 2 and < 4 < 2 	Treatment period	Categorical descriptives
Average number of attacks treated with study treatment per month ¹	
For all participants:
 
 ≥ 8 ≥ 6 and < 8 ≥ 4 and < 6 ≥ 2 and < 4 < 2 
Subgroup analyses:
 
 by Sex by Age Group: <40 vs ≥40 by Age Group: <65 vs ≥65 by Race White vs All other races by CV risk category by renal function class 	Treatment period	Categorical descriptives
Maximum number of attacks treated with study treatment per	
 ≥ 8 ≥ 6 and < 8 ≥ 4 and < 6 	Treatment period	Categorical descriptives

Parameter	Description	Timing	Methodology
month, defined as maximum of monthly total number attacks treated with study treatment among months 1-12 for each participant ¹	
 • ≥ 2 and < 4 • < 2 		
Number of months with the number of attacks treated with study treatment in each category ¹	For each category: 
 • ≥ 8 • ≥ 6 and < 8 • ≥ 4 and < 6 • ≥ 2 and < 4 • < 2 	Treatment period	Categorical descriptives
Average number of study treatment taken per month ¹	
 • ≥ 16 • ≥ 14 and < 16 • ≥ 12 and < 14 • ≥ 10 and < 12 • ≥ 8 and < 10 • ≥ 6 and < 8 • ≥ 4 and < 6 • ≥ 2 and < 4 • < 2 	Treatment period	Categorical descriptives

Analysis visits defined in Section 6.2.2.

¹ Participants in the ubrogapant treatment arms only. No imputation for the last incomplete month.

Treatment compliance for this study will be summarized as follows:

Table 5-18 Treatment Compliance Summaries

Parameter	Description	Timing	Methodology
Overdosing ¹	Participants who took more than 2 doses within 48 hours or 2 calendar days (if time information is not available)		Listing

¹ Participants in the ubrogapant treatment arms only.

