TEAEs	Summary by 
 • SOC and PT for all participants and by subgroup analyses: 
 ○ by Sex ○ by Age Group <40 vs \geq40 ○ by Age Group <65 vs \geq65 ○ by Race White vs All other races ○ by cardiovascular risk category ○ by renal function class • SOC and PT for concomitant medication classes used by at least 10% of participants in at least one treatment group • SOC, PT, and AE onset time intervals 
 ○ <3 months ○ \geq3 and <6 months ○ \geq6 and <9 months ○ \geq9 and <12 months ○ \geq12 months • SOC, PT, and average number of migraine attacks treated with study treatment per month 
 ○ \geq2 ○ \geq4 ○ \geq6 	From randomization date to Visit 16 for participants with Visit 16, or within 30 days after last visit or last treatment, whichever is later, for participants without Visit 16	Categorical descriptives

Parameter	Description	Timing	Methodology
	
 ○ ≥8 • SOC, PT, and severity • SOC, PT, and causal relationship to the study treatment • Type (Mild, Moderate, Severe, related, not related) • SOC and PT for TEAEs occurring in ≥ 2% of participants in any ubrogapant treated dose group (and greater than placebo) 		
Common TEAEs	Summary by PT 
 • Includes TEAEs occurring in ≥ 2% of participants in any treatment group 	From randomization date to Visit 16 for participants with Visit 16, or within 30 days after last visit or last treatment, whichever is later, for participants without Visit 16	Categorical descriptives
On-therapy SAEs ¹	Overall summary and by PT	From randomization date to Visit 16 for participants with Visit 16, or within 30 days after last visit or last treatment, whichever is later, for participants without Visit 16	Categorical descriptives
On-therapy fatal SAEs	Participants who report On-therapy fatal SAEs will have their fatal SAEs and all AEs listed	From randomization date to Visit 16 for participants with Visit 16, or within 30 days after last visit or last treatment, whichever is later, for participants without Visit 16	Categorical descriptives
AEs leading to discontinuation ²	Overall summary and by PT	From randomization date to Visit 16 for participants with Visit 16, or within 30 days after last visit or last treatment, whichever is later, for participants without Visit 16 ²	Categorical descriptives

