5.1.1.6 Interim Analyses

The interim analysis will occur when at least 300 ubrogepant participants (with a minimum of 2 migraines treated with ubrogepant per month, on average) have been enrolled in the study for 6 months, and 200 ubrogepant participants (with a minimum of 2 migraines treated with ubrogepant per month, on average) have been enrolled in the study for 1 year.

The treatment assignments will be unblinded to the Allergan staff for the interim analyses. The interim analyses will include all analyses specified in this SAP except for efficacy analyses.

[REDACTED]

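### TEAEs by attack frequency are planned in nested rows (≥2, ≥4, ≥6, ≥8 per month) with no <2 group, which weakens the visible use-harm gradient; the SAP's own disjoint bins should be added

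*SAP*

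**What the plan says.** SAP Section 5.1.1.4.2 (Table 5-20) lists, among the TEAE summaries, one by "SOC, PT, and average number of migraine attacks treated with study treatment per month". Its categories are ≥2, ≥4, ≥6 and ≥8. None has an upper bound and there is no category below 2.

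Two other places in the SAP handle a similar split differently:

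- Section 5.1.1.4.1 (Table 5-17) summarises "Average number of attacks treated with study treatment per month" in five disjoint bins: <2, ≥2 and <4, ≥4 and <6, ≥6 and <8, and ≥8.
- The same TEAE cell of Table 5-20 has a summary by "SOC, PT, and AE onset time intervals", and those intervals are also disjoint.

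The method for Table 5-20 is categorical descriptives, defined in Section 5.1.1.1.3 as "Number and percentage of participants in individual categories", with each participant counted once per category. No test or trend model is attached.

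**The concern.** A participant averaging 8 treated attacks a month is counted in all four rows; one averaging 1.5 is counted in none. Each lower row therefore contains the heavier users it would be compared with, and the lightest users, who are the natural reference group, are missing.

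The primary objective is the safety of intermittent treatment over one year, so frequency of dosing is a central exposure variable. If TEAEs for some preferred term rise with use, the planned rows will show a smaller difference than disjoint bins would. If the risk changes at about 2 attacks a month, the planned rows will look flat. In either case the reader could be falsely reassured by a table whose apparent purpose is to show whether more use brings more events.

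**Working it through.** The SAP states no rate or expected distribution for this table, so there is no figure of the plan's to reproduce.

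**Inputs from the documents.** The nested cut-points (Table 5-20); the disjoint bins (Table 5-17); 400 patients per arm (Protocol 4.1); a cap of 8 treated attacks per 4 weeks (Protocol 5.6.1); 30-day months (SAP Table 6-5).

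**Assumed inputs.** The share of participants in each bin and the TEAE rate in each bin. Every share and rate below is an assumption, listed in the order <2, 2 to <4, 4 to <6, 6 to <8, ≥8.

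**1. Identity, needing no assumption.** Let w be the share of the ≥2 group who average ≥8. Then

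rate(≥2) = w × rate(≥8) + (1 − w) × rate(2 to <8),

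so rate(≥8) − rate(≥2) = (1 − w) × [rate(≥8) − rate(2 to <8)].

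**2. One worked example.** Shares 30/35/20/10/5%, rates 50/55/60/65/70%.

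- ≥2: (35×55 + 20×60 + 10×65 + 5×70)/70 = 4125/70 = 58.9%
- ≥4: (20×60 + 10×65 + 5×70)/35 = 2200/35 = 62.9%
- ≥6: (10×65 + 5×70)/15 = 1000/15 = 66.7%
- ≥8: 70.0%

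The planned contrast, ≥8 versus ≥2, is 70.0 − 58.9 = 11.1 points. The disjoint contrast over the same range, ≥8 versus 2 to <4, is 70 − 55 = 15 points. Nesting therefore removes 3.9 of 15 points, about 26%. With a <2 bin the contrast would be 70 − 50 = 20 points, so omitting <2 hides a further 5.

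Check on the identity: w = 5/70 = 0.071; rate(2 to <8) = 3775/65 = 58.1%; 0.929 × 11.9 = 11.1 points.

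**3. Sensitivity to the use distribution.** Rates 2/4/6/8/10%. The disjoint contrasts are fixed at 6 points for ≥8 versus 2 to <4 (ratio 2.5) and 8 points for ≥8 versus <2 (ratio 5.0).

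| Assumed shares (%) | rate(≥2) | ≥8 minus ≥2 | Ratio ≥8 to ≥2 |
|---|---|---|---|
| 50/30/13/5/2 | 5.16% | 4.84 points | 1.94 |
| 35/35/18/9/3 | 5.38% | 4.62 points | 1.86 |
| 20 each | 7.00% | 3.00 points | 1.43 |
| 10/15/25/30/20 | 7.22% | 2.78 points | 1.38 |

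If risk rises only in the top bin (2/2/2/2/10%), the ratio of ≥8 to ≥2 is 4.31, 4.22, 2.50 and 2.65 for the same four distributions, against a disjoint ratio of 5.0.

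**4. A step at 2 attacks.** Rates 1/4/4/4/4%. The planned rows read 4/4/4/4% under every distribution, so the fourfold step does not appear.

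**5. Can the disjoint bins be recovered?** Take 400 in an arm, shares 35/35/18/9/3% and rates 2/4/6/8/10%, with expected events rounded. For all, ≥2, ≥4, ≥6 and ≥8, the denominators are 400/260/120/48/12 and the events 17/14/8/4/1. Subtracting adjacent entries gives 3/140, 6/140, 4/72, 3/36 and 1/12, the five disjoint bins. The <2 bin is the all-participants table minus the ≥2 row.

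**6. Size of the top bin.** The cap equals 8 × 30/28 = 8.57 attacks per 30-day month. Averaging ≥8 therefore needs at least 8/8.57 = 93% of the maximum, so that group may well be small.

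**The case against.** The strongest reply is that nothing is lost. Average use is a participant-level variable, each participant is counted once per row, and counts are reported with percentages. The same cell also plans TEAEs for all participants, so every disjoint bin, including <2, follows by subtraction, as step 5 shows. This stands: the weakness is one of presentation. What remains is that the subtraction must be repeated for every preferred term and each dose arm, when the bins already exist in the SAP.

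The cumulative form also has a purpose. The interim analysis counts ubrogepant participants "with a minimum of 2 migraines treated with ubrogepant per month, on average", and Table 5-17 has a separate row for those averaging at least 2 attacks. A ≥2 row gives TEAEs for that qualifying group, and cumulative cuts keep the sparse upper groups larger. This is a good reason to keep the nested rows. It does not explain leaving out the bins.

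A reader might infer that the table cannot show any relation between use and harm, or that it is the plan's only look at repeated use. The documents support neither. A steady rise across bins still rises across the nested rows (58.9, 62.9, 66.7 and 70.0% in the example). TEAEs are also planned by onset interval and by randomised dose, and dosing times are overlaid on liver-test plots for participants with ALT or AST ≥3 × ULN.

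A reader might also set 11.1 points against 20 and call it a 45% loss. That merges nesting (15 to 11.1 points, about 26%) with the missing <2 group (the other 5 points), and all of it rests on assumed inputs.

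Finally, disjoint bins would not give a clean exposure-response comparison. Average use arises after randomisation and is tied to migraine frequency and time on study. That is true of either layout and should be stated with the table.

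**Conclusion.** The point holds as a moderate reporting weakness in a descriptive table. The rows are nested, <2 is absent, and the SAP handles the same variable better elsewhere. The direction of the effect does not depend on the assumptions: the identity shrinks the ≥8 versus 2-to-<8 contrast by (1 − w) whatever the distribution. The size does depend on them. Across the four assumed distributions with steadily rising rates, a 6-point contrast becomes 2.78 to 4.84 points; a step at 2 attacks disappears altogether unless the reader subtracts. No planned test or decision is affected: the SAP's general statement that "All statistical tests will be 2-sided hypothesis tests performed at the 5% level of significance for main effects" does not reach this summary, which is purely descriptive. The table shells are in a separate document that is not available here and may already show more than the SAP text does.

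**What to change.** In Table 5-20, add to the TEAE summary by average attacks treated the five disjoint bins of Table 5-17, including <2, for the ubrogepant arms, by dose and pooled over doses. Keep the cumulative rows, because ≥2 matches the SAP's own exposure threshold. Add a footnote that the comparison is descriptive and non-randomised, since use is a post-randomisation variable.

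This needs SAP wording and a matching table shell, with no new data or derivation. The cost is a larger table whose percentages in the top bins will be sparse and unstable. The planned ≥8 row already has that limitation, since it is the same group.

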5.1.1.4.3 Clinical Laboratory Assessments

Clinical laboratory assessments will be summarized by treatment group for the Safety Population as follows:

Table 5-21 Clinical Laboratory Summaries

Endpoint	Description	Timing	Methodology
Number and percentage of participants with Potentially Clinically Significant (PCS) values ¹	Summary by laboratory category, parameter, and PCS criteria 
 Parameters and PCS criteria specified in Section 6.3.5.1 N1 (percentage denominator) = Participants with non-missing non-PCS baseline and ≥ 1 postbaseline parameter assessment 	Randomization to End of Study ³	PCS descriptives
Descriptives ²	Summary by laboratory category and parameter in SI units and in conventional units and analysis visit 
 Parameters specified in Section 6.3.5.3 	Randomization to End of Study ³	CFB descriptives
Shift from baseline	Summary by laboratory parameter and category 
 Low, normal, and high categories provided by central laboratory Parameters specified in Section 6.3.5.3 	End of Study ³	Shift analysis
Liver function findings ⁴	Summary of number and percentage by hepatic laboratory parameter and PCS categories. Definition of PCS categories see Table 6-10 in Section 6.3.4.2.	Randomization to End of Study ³	Categorical descriptives
Adjudication results of ALT or AST elevations ⁵	Summary of relationship of ALT or AST elevation to study medication for participants with adjudicated case (i.e., ALT $\geq 3 \times$ ULN and/or AST $\geq 3 \times$ ULN) by the following categories: 
 Probable Possible Unlikely Insufficient data Summary will be provided for the incidence by number of participants and by number of events	Randomization date to End of Study ³	Categorical descriptives

ALT = aspartate aminotransferase; AST = aspartate aminotransferase; TBL = total bilirubin; ALP = alkaline phosphatase; INR = international normalized ratio; ULN = upper limit of normal.

¹ Participants who report ≥ 1 postbaseline PCS value will have their laboratory visits with PCS values and all AEs listed.

² Clinical laboratory results and comments will be listed.

³ Analysis visits defined in Section 6.2.2.

Endpoint	Description	Timing	Methodology
----------	-------------	--------	-------------

⁴ Details of all participants with any liver function laboratory findings will be listed. For participants who met ALT $\geq 3 \times \text{ULN}$ or AST $\geq 3 \times \text{ULN}$, their ALT, AST, TBL, ALP, and INR assessments, and all AEs will be listed for all study visits. In addition, if available, their abnormal liver biochemistries risk factors, liver disease signs and symptoms, liver diagnostic tests, specialist consultation, liver lab tests, and drug screen will also be listed.

⁵ Participants with at least one adjudicated case (i.e. ALT $\geq 3 \times \text{ULN}$ or AST $\geq 3 \times \text{ULN}$) will be listed with their ALT and AST assessments, adjudication dates, adjudication results and confounding factors for all study visits.

Evaluation of drug-induced serious hepatotoxicity (eDISH) plot (scatter plot of maximum total bilirubin vs. maximum ALT) will be generated. The ALT, AST, total bilirubin, and ALP values over time will be overlaid on the same plot along with indicators for dosing times for each participant with ALT or AST elevation ($\geq 3 \times \text{ULN}$).

5.1.1.4.3.1 Potential Hy's Law

Potential Hy's Law criteria will be summarized by treatment group for the Safety Population as follows:

Table 5-22 Potential Hy's Law Summaries

Endpoint	Description	Timing	Methodology
Potential Hy's Law within 24-hour window	Number and percentage of participants with postbaseline assessment of the following laboratory parameters based on blood draws collected within a 24-hour period: 
 ALT or AST $\geq 3 \times \text{ULN}$ TBL $\geq 2 \times \text{ULN}$ ALP $< 2 \times \text{ULN}$ 	Randomization to End of Study ¹	Categorical descriptives
Potential Hy's Law without window (e-DISH)	Number and percentage of participants with postbaseline assessment of the following laboratory parameters at any time: 
 Maximum ALT or AST $\geq 3 \times \text{ULN}$ Maximum TBL $\geq 2 \times \text{ULN}$ 	Randomization to End of Study ¹	Categorical descriptives

e-DISH = evaluation of drug-induced serious hepatotoxicity.

ALT = alanine aminotransferase; AST = aspartate aminotransferase; TBL = total bilirubin.

ALP = alkaline phosphatase; ULN = upper limit of normal.

¹ Analysis visits defined in Section 6.2.2.

Participants who meet the Potential Hy's Law criteria will have their ALT, AST, TBL, and ALP assessment listed for all study visits.

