7.3.2.3 Clinical Laboratory Parameters

Descriptive statistics for clinical laboratory values (in SI units) and changes from the baseline values at each assessment timepoint will be presented by treatment group for clinical laboratory parameters. In addition, descriptive statistics for values and changes from the baseline values in conventional units at each assessment timepoint will be presented for selected clinical laboratory parameters. Patient narratives will also include the values in conventional units for the selected laboratory parameters.

Clinical laboratory test values will be considered potentially clinically significant (PCS) if they meet either the lower-limit or higher-limit PCS criteria. PCS criteria will be specified in the Statistical Analysis Plan (SAP). The number and percentage of patients who have PCS postbaseline clinical laboratory values will be tabulated by treatment group. The percentages will be calculated relative to the number of patients with available non-PCS baseline values and at least 1 postbaseline assessment. The numerator will be the total number of patients with available non PCS baseline values and at least 1 PCS postbaseline value. A supportive tabular display of patients with PCS postbaseline values will be provided, including the

patient number, baseline, and all postbaseline (including non-PCS) values. In addition, a tabular display showing all AEs that occurred in patients who had PCS postbaseline clinical laboratory values will be provided.

Shift tables from baseline to end of study for clinical laboratory parameters will be presented by treatment group for the following categories: low, normal, and high, which are provided by the lab vendor.

Any post-treatment ALT and/or AST results that are ≥ 3 times the ULN are considered events of clinical interest in this study and are subject to blinded adjudication by the Clinical Adjudication Committee to determine whether the elevation is due to treatment or not, and to determine whether there is a confounding factor. Patients with liver function laboratory findings that meet predetermined criteria will be summarized by treatment group along with the adjudication results. A detailed listing of all patients with any liver function laboratory findings will be provided.

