6.3.5.2 Hepatic Laboratory Abnormalities

The selected event is of clinical interest: Elevated ALT or AST lab value that is ≥ 3 times the ULN. The following laboratory parameters will be summarized:

Table 6-13 Criteria for Hepatic Laboratory Abnormalities

Laboratory Parameter	Categories
ALT	>= 1 × ULN
	>= 1.5 × ULN
	>= 2 × ULN
	>= 3 × ULN
	>= 5 × ULN
	>= 10 × ULN
	>= 20 × ULN
AST	>= 1 × ULN
	>= 1.5 × ULN
	>= 2 × ULN
	>= 3 × ULN
	>= 5 × ULN
	>= 10 × ULN
	>= 20 × ULN
ALT or AST	>= 1 × ULN
	>= 1.5 × ULN
	>= 2 × ULN
	>= 3 × ULN
	>= 5 × ULN
	>= 10 × ULN
	>= 20 × ULN
Bilirubin Total	>= 1 × ULN
	>= 1.5 × ULN
	>= 2 × ULN
	>= 3 × ULN
	>= 5 × ULN
	>= 10 × ULN
	>= 20 × ULN
Alkaline Phosphatase	>= 1 × ULN
	>= 1.5 × ULN
	>= 2 × ULN
	>= 3 × ULN
	>= 5 × ULN

Laboratory Parameter	Categories
	$\geq 10 \times \text{ULN}$
	$\geq 20 \times \text{ULN}$
Concurrent Elevations ¹	ALT or AST $\geq 3 \times \text{ULN}$ AND Bilirubin Total $\geq 1.5 \times \text{ULN}$
	ALT or AST $\geq 3 \times \text{ULN}$ AND Bilirubin Total $\geq 2 \times \text{ULN}$
Potential Hy's Law ¹	ALT or AST $\geq 3 \times \text{ULN}$ AND Bilirubin Total $\geq 2 \times \text{ULN}$ AND ALP $< 2 \times \text{ULN}$

LLN = lower limit of normal (value provided by the laboratory); PCS = potentially clinically significant; SI = Le Système International d'Unités (International System of Units); ULN = upper limit of normal (value provided by the laboratory).

¹ Elevations are from the same day

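### The liver threshold row of SAP Table 5-21 neither sets aside baseline elevations nor limits its denominator to participants tested after randomization, so its 1 to 2 × ULN rows are hard to compare between arms

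*SAP*

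**What the plan says.** Three parts of the SAP fix how the liver table is computed.

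- **The row.** SAP 5.1.1.4.3, Table 5-21, describes the liver findings as a "Summary of number and percentage by hepatic laboratory parameter and PCS categories", timed "Randomization to End of Study", with Categorical descriptives as the method. It states no N1 of its own.
- **The method.** In SAP 5.1.1.1.3, Table 5-2, Categorical descriptives is M2. Its standard denominator is the analysis population. The only alternative it offers is "N1 = participants with non-missing baseline value".
- **The cut-offs.** SAP 6.3.5.2, Table 6-13, lists ALT, AST, ALT or AST, total bilirubin and alkaline phosphatase, each at 1, 1.5, 2, 3, 5, 10 and 20 × ULN and above. The row itself points elsewhere, to Table 6-10 in Section 6.3.4.2, which holds adverse event groupings.

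The PCS row of the same Table 5-21 is built differently: "N1 (percentage denominator) = Participants with non-missing non-PCS baseline and ≥ 1 postbaseline parameter assessment". That matches M3 in Table 5-2 ("Percentage denominator = number of participants with all non-missing non-PCS baseline and ≥ 1 non-missing postbaseline assessment") and Protocol 7.3.2.3, which says of PCS laboratory values: "The percentages will be calculated relative to the number of patients with available non-PCS baseline values and at least 1 postbaseline assessment".

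Baseline is the last value before the first lead-in dose (SAP Table 5-16). The Safety population takes all randomized usual-care patients, but only ubrogepant patients who took a dose (Protocol 7.1.2).

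**The concern.** The liver row calls its thresholds PCS categories, yet it lacks the two conditions that the plan attaches to PCS percentages elsewhere. This has two consequences.

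First, a participant who entered with, say, ALT at 1.2 × ULN and shows it again at any later visit is counted in the 1 × ULN row, in whichever arm. Such participants add the same background to both arms and pull the ratio of ubrogepant to usual care towards 1.

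Second, a participant with no test after randomization sits in the denominator and can never reach the numerator, so is treated as free of elevation.

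The topic matters for this drug. Protocol Section 1 reports that two earlier CGRP antagonists were stopped after ALT increases, and Section 3.1 sets up an adjudication committee for transaminase elevations. The usual-care arm exists to give a background against which safety findings can be read, and the liver table is one place where that comparison is made.

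**Working it through.** The documents give no expected liver rate, baseline prevalence or untested share, so there is no stated figure to reproduce. What follows is illustration; every rate in it is an assumption.

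**Baseline part.** Let b be the share at or above the cut-off at baseline and seen there again after randomization (full persistence), and r the new-onset risk among the rest. With everyone tested:

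- rate under M2 = b + (1 − b) × r
- rate with baseline elevations set aside = r
- risk difference under M2 = (1 − b) × (r on ubrogepant − r on usual care)

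With r = 20% on ubrogepant and 10% on usual care (true ratio 2.0, true difference 10 points):

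| b | Ubrogepant | Usual care | Ratio | Difference |
|---|---|---|---|---|
| 0 | 20.0% | 10.0% | 2.00 | 10.0 |
| 5% | 0.05 + 0.95 × 0.20 = 24.0% | 0.05 + 0.95 × 0.10 = 14.5% | 1.66 | 9.5 |
| 10% | 0.10 + 0.90 × 0.20 = 28.0% | 0.10 + 0.90 × 0.10 = 19.0% | 1.47 | 9.0 |
| 15% | 0.15 + 0.85 × 0.20 = 32.0% | 0.15 + 0.85 × 0.10 = 23.5% | 1.36 | 8.5 |

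With r = 10% v 5% the pattern is the same: the ratio reads 1.49, 1.31 and 1.22 at b = 5, 10 and 15%, and the difference 4.75, 4.5 and 4.25 points against 5. If no baseline elevation were ever seen again, both rates would be (1 − b) × r and the ratio would stay at 2.0. Partial persistence, if equal between arms, lies between these limits.

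**Higher cut-offs.** What moves the ratio is b relative to r. Protocol 6.2.3 excludes laboratory abnormalities judged clinically significant at Screening, so b should be close to zero at 3 × ULN and above, although the visible text gives no numeric limit. If b were 0.5% with r = 3% v 1%, the rates would be 3.485% v 1.495%: the ratio reads 2.33 instead of 3.00, and the difference 1.99 points instead of 2.

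**Untested part.** Let m be the share with no post-baseline value. The rate is multiplied by (1 − m).

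- Equal m: the ratio is unchanged. At m = 10% in both arms, a 5.0-point difference reads 4.5.
- m = 10% in usual care, 2% on ubrogepant: the ratio is multiplied by 0.98 / 0.90 = 1.089. A true 1.00 reads 1.09 and a true 2.00 reads 2.18.
- Shares reversed: the factor is 0.90 / 0.98 = 0.918, and a true 2.00 reads 1.84.

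Unequal shares are plausible because the two Safety population rules differ.

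**What the other planned outputs cover.**

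- The PCS table conditions on baseline and a later test, but for ALT and AST only above 3 × ULN (Table 6-12). It covers bilirubin above 1.5 × ULN and alkaline phosphatase above 3 × ULN.
- The shift table shows normal to high, but at End of Study only, which SAP 6.2.2 defines as the last available assessment. A rise that resolves is missed.
- Change-from-baseline tables give means, medians and ranges by visit, not incidence.
- Adjudication starts at 3 × ULN.

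No table in the visible plan gives the incidence of peak ALT or AST at 1, 1.5 or 2 × ULN among participants who were below that level at baseline.

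**The case against.** The case against is substantial, and much of it stands.

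- **The event of interest lies higher.** SAP 6.3.5.2 states: "The selected event is of clinical interest: Elevated ALT or AST lab value that is ≥ 3 times the ULN". There the dilution should be small, and the PCS table and blinded adjudication give separate readings. This stands, and it confines the point mainly to the low rows.
- **Pre-existing elevations do not count automatically.** A reader might infer that anyone high at baseline is a finding. The row's timing does not support that: the value must be measured again after randomization.
- **A true effect need not be hidden.** A reader might infer that the table must mask a ubrogepant effect. The documents give neither baseline prevalence nor persistence. Randomization should balance baseline elevations on average, the table carries no test, and in the main illustration 85 to 95% of the risk difference survives. Untested participants can push the ratio up as well as down, so dilution is the wrong word for that part.
- **The SAP does not breach the protocol.** The baseline condition in Protocol 7.3.2.3 is written for PCS values. Its separate sentence on liver findings asks only for a summary by treatment group with the adjudication results. The charge is an unexplained difference within Table 5-21, not a contradiction.
- **Table specifications are in a separate document** (SAP Section 4). N1 could be refined there, but the SAP as written assigns M2.

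Two further complaints carry little weight. Counting a value exactly equal to ULN in the lowest row is trivial. The PCS row (above 3 × ULN) and the liver row (3 × ULN or more) serve different purposes, so different counts are to be expected.

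**Conclusion.** The point holds as a limited one about the denominator and the handling of baseline. The liver row mixes new elevations with persisting ones and counts untested participants as normal, while the PCS row beside it does neither. The consequence falls mainly on the 1, 1.5 and 2 × ULN rows, where the shift and change-from-baseline outputs fill the gap only in part.

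The size is not known from the documents. Under the main assumptions above, the ratio falls from 2.0 to between 1.66 and 1.36, while the difference loses at most 1.5 of 10 points. Any bias from untested participants depends on how the untested shares differ between arms, and its direction is open. The plan's assessment of marked transaminase elevations is largely unaffected. The change is worth making because it is cheap and makes the low rows interpretable.

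**What to change.** In SAP Table 5-21, give the liver row its own denominators for each single-parameter cut-off in Table 6-13:

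1. Add a count and percentage with N1 = participants below that cut-off at baseline and with at least one post-baseline value of that parameter.
2. Keep the count that ignores baseline beside it, with N1 = participants with at least one post-baseline value of that parameter.
3. Change the reference for the cut-offs from Table 6-10 (Section 6.3.4.2) to Table 6-13 (Section 6.3.5.2).

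Because baseline precedes the first lead-in dose, setting aside baseline elevations does not remove any that arose on lead-in treatment. All the data are already collected. The cost is SAP wording, some programming and a slightly longer descriptive table; the second count stays available for comparison with other studies.
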